6.3.2.2. Concomitant Therapies Requiring Careful Monitoring (Use with Caution)

Based on the results of in vitro and in vivo studies, the following therapies should be avoided and replaced with alternative treatments. If this is not possible, participants receiving these drugs should be carefully monitored.

- Concomitant use of drugs with a potential for QT prolongation should be avoided and replaced with alternative treatments. If this is not possible, subjects receiving these drugs

should be adequately monitored by ECG controls, drug concentration (where applicable), and serum electrolytes (*i.e.*, potassium and magnesium).

These medications include but are not limited to:

- Fluoroquinolones such as, ciprofloxacin and moxifloxacin.
- Azole antifungals such as fluconazole and posaconazole.
- Serotonin (5-HT3) antagonists such as granisetron and ondansetron. See [Appendix 10](#), Table 4 for a complete list of medications known to prolong the QT interval.

- Moderate or strong inhibitors of CYP3A4: Ivosidenib clinical trials and physiologically based pharmacokinetic simulations have shown that ivosidenib plasma concentrations increase with co-administration of a strong or moderate CYP3A4 inhibitor, and increased ivosidenib plasma concentrations may increase the risk of QTc prolongation. Therefore, alternative therapies that are not moderate or strong CYP3A4 inhibitors should be considered during treatment with ivosidenib. If concomitant use of moderate CYP3A4 inhibitors is unavoidable, subjects should be monitored for increased risk of QTc prolongation. If a strong CYP3A4 inhibitor must be co-administered, reduce the ivosidenib dose to 250 mg QD. If the strong inhibitor is discontinued, increase the ivosidenib dose (after at least 5 half-lives of the strong CYP3A4 inhibitor) to the recommended dose of 500 mg QD (see Table 5 in [Appendix 10](#)).
- Sensitive substrates of CYP2C9: Ivosidenib may also induce CYP2B6, CYP2C8, and CYP2C9. Consider alternative therapies that are not sensitive substrates of CYP2C9 (*e.g.*, phenytoin, warfarin). Monitor INR levels more frequently in subjects receiving warfarin (a CYP2C9 substrate) during initiation or discontinuation of ivosidenib.
- Coadministration of ivosidenib may decrease the concentrations of hormonal contraceptives. Consider alternative methods of contraception in subjects receiving ivosidenib as described [Appendix 7](#).

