6.3.2. Concomitant Medications and Procedures

All medications (other than IMPs) and significant non-drug therapies (including physical therapy, IV medications and fluids, herbal/natural medications, over-the-counter medications, and blood transfusions) administered during the study must be listed in the eCRF. If changes

occur during the study period, documentation of drug dosage, frequency, route, and date should also be included on the eCRF. The Investigator should instruct the subject not to take any additional medications (including over-the-counter products) during the study without prior consultation with the Investigator. In general, the use of any concomitant medication deemed necessary for the care of the subject is permitted in this study, except as specifically prohibited in Section 6.3.2.1. Information on prior anti-neoplastic treatment received for the primary diagnosis including prior radiation therapy will be collected.

A list of prohibited and unauthorized treatments by drug class can be consulted in the eCRF.

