Appendix 7: Contraception Considerations

Definition of women of childbearing potential and contraception methods

Women of childbearing Potential

A woman is considered of childbearing potential (WOCBP), *i.e.*, fertile, following menarche and until becoming postmenopausal unless permanently sterile. Permanent sterilization methods include hysterectomy, bilateral salpingectomy and bilateral oophorectomy. A postmenopausal state is defined as no menses for 12 months without an alternative medical cause.

Contraception methods

Definition of highly effective contraception methods for the study:

Highly effective methods of birth control refer to those which result in a low failure rate (*i.e.* less than 1% per year), when used consistently and correctly, such as combined hormonal contraception associated with inhibition of ovulation (oral, intravaginal, transdermal), progestogen-only hormonal contraception when associated with inhibition of ovulation (oral, injectable, implantable), some intra-uterine devices, intrauterine hormone-releasing system, true sexual abstinence (when this is in line with the preferred and usual lifestyle of the participant), bilateral tubal occlusion, male sterilization (vasectomy).

Definition of acceptable contraception methods for the study:

Acceptable contraception methods for the study are those considered as highly effective methods, male or female condom with or without spermicide, cap, diaphragm or sponge with spermicide.

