Appendix 13: Local modification of the clinical study protocol (GBR)

FINAL VERSION DATE:	20 December 2023
COUNTRY CONCERNED:	United Kingdom
CENTRES CONCERNED:	All centres in United Kingdom
NATURE OF MODIFICATIONS	

- Update of inclusion criteria 4 and Appendix 7 to clarify acceptable contraception methods.- In line with CTFG guidance, an additional pregnancy test to be performed at the end of the relevant systemic exposure; at the 100-day safety follow up visit.- Clarification added to section 8.4 that all SAEs must be reported to the sponsor immediately and within 24 hours of awareness at the latest.	

Paragraph impacted 5.1 Inclusion Criterion- 4 - Sex and Contraceptive/Barrier requirements
Amended text:

Women of childbearing potential (WOCBP) must agree to abstain from sexual intercourse or to use 2 forms of contraception, one of which must be highly effective and one a barrier method (Appendix 7) highly effective (Appendix 7) forms of contraception, at least one of which must be a barrier method, from the time of giving informed consent throughout the study, and for 5 months after the last dose of study treatment.

Paragraph impacted Appendix 7 - Contraception considerations
Amended text:

Definition of acceptable contraception methods for the study: ~~Acceptable contraception methods for the study are those considered as highly effective methods~~, In addition to a highly effective method, the second form of contraception may include male or female condom with or without spermicide, cap, diaphragm or sponge with spermicide.

Paragraph impacted 4.1.2 Investigational Schedule

Amended text: a new cross (X) is present in the Table (4.1.2) 1 column safety follow-up 100 (+5) Days After Last Nivolumab Dose and line pregnancy test.

Table (19) 1 - Schedule of Assessments for Subjects in the Safety Lead-in Phase and Expansion Phase

Visit/Cycle	Screening ¹	Cycle 1 (21 Days)			Cycle 2 (21 Days)		Cycles 3 and 4 (21 Days)	Cycle 5 and Beyond (28 Days Each Cycle)	End of Treatment ²	Safety Follow-up ²		PFS Follow-up ³	Survival Follow-up
Study Day	D-28 to D-1	D1	D8	D15 (± 2 Days)	D1 (± 2 Days)	D15 (± 2 Days)	D1 (± 2 Days)	D1 (± 2 Days)	Within 7 Days After Last Dose	30 (+5) Days After Last Dose	100 (+5) Days After Last Nivolumab Dose		Every 12 weeks (± 2 weeks)
Allocation to IMP ⁴		X			X		X	X					
Informed Consent	X												
Inclusion/Exclusion Criteria	X												
Demographics	X												
Disease History	X												

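### Section 6.3.2.2 warns that ivosidenib may weaken hormonal contraception, but Appendix 7 lists hormonal methods as highly effective with no caveat, so a hormonal method plus a barrier can satisfy UK criterion 4

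*Protocol*

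**What the plan says.** **The warning.** Protocol Section 6.3.2.2 lists therapies to be used with caution. Its lead-in says that "the following therapies should be avoided and replaced with alternative treatments. If this is not possible, participants receiving these drugs should be carefully monitored". The last bullet reads "Coadministration of ivosidenib may decrease the concentrations of hormonal contraceptives", followed by "Consider alternative methods of contraception in subjects receiving ivosidenib as described" and a reference to Appendix 7.

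**The general rule on other medicines.** Section 6.3.2 says that "the use of any concomitant medication deemed necessary for the care of the subject is permitted in this study, except as specifically prohibited". The prohibitions are those listed under Section 6.3.2.1, which does not name hormonal contraceptives.

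**The list of methods.** Appendix 7 calls a method highly effective if its failure rate is "less than 1% per year), when used consistently and correctly, such as combined hormonal contraception associated with inhibition of ovulation". It continues with "progestogen-only hormonal contraception when associated with inhibition of ovulation", then "some intra-uterine devices, intrauterine hormone-releasing system, true sexual abstinence", bilateral tubal occlusion and vasectomy. Neither ivosidenib nor reduced hormone exposure is mentioned.

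**The UK rule.** Under Appendix 13, women of childbearing potential in the UK must abstain or use "2 forms of contraception, one of which must be highly effective and one a barrier method", with a reference to Appendix 7. The UK edit rewrites the Appendix 7 paragraph on acceptable methods and leaves the definition of highly effective methods as it was.

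**The concern.** A reader who follows the cross-reference from Section 6.3.2.2 to find the alternatives arrives at a list that opens with the methods just warned about. The non-hormonal methods are in the list, but nothing marks them as the alternatives.

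In the UK this reaches an eligibility rule. The rule wants a highly effective method in addition to a barrier, so the barrier alone is not the protection it intends. If the highly effective half is a hormonal method and hormone levels fall on ivosidenib, the woman may in practice be relying on the barrier.

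What is at stake is participant safety, not inference: inclusion criterion 4 itself says that all three study drugs may harm a fetus.

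**Working it through.** The plan states no figure to reproduce. The check sets the texts side by side and adds two short counts.

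**Step 1. Does anything in the protocol remove credit from hormonal methods?**

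| Place | What it does | Changes what criterion 4 counts? |
|---|---|---|
| 6.3.2.2, lead-in | Avoid and replace; monitor if that is not possible | No |
| 6.3.2.2, contraceptive bullet | Advises considering other methods; refers to Appendix 7 | No |
| 6.3.2 | Allows necessary medicines unless 6.3.2.1 prohibits them | No |
| 6.3.2.1 | Does not name hormonal contraceptives | No |
| Appendix 7 | Lists hormonal methods under a general definition | No ivosidenib caveat |
| Appendix 13 (UK) | One highly effective method plus one barrier | Relies on the unchanged list |

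Other bullets in 6.3.2.2 say what to monitor: ECG and electrolytes for QT-prolonging drugs, QTc for moderate CYP3A4 inhibitors, INR for warfarin. The contraceptive bullet names no monitoring, so the fallback in the lead-in has no content for this item.

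**Step 2. Why the UK rule is the clear case.** The global criterion 4 (Section 5.1) asks for two highly effective forms, at least one of them a barrier. Appendix 7 does not class any barrier as highly effective, so the global wording cannot be applied literally. The UK wording separates the two roles, and a hormonal method plus a condom fits it.

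**Step 3. Count of methods.** Appendix 7 names seven highly effective methods: (1) combined hormonal, (2) progestogen-only hormonal, (3) some intra-uterine devices, (4) intrauterine hormone-releasing system, (5) true abstinence, (6) bilateral tubal occlusion, (7) vasectomy.

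- Lose credit under the fix: methods 1 and 2, so 2.
- Left to the clinical team: method 4, so 1.
- Unchanged: 7 − 2 − 1 = 4.

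**Step 4. How long after treatment?** The existing contraception period is 5 months after the last dose of study treatment. Section 2.2.2 gives a mean terminal half-life of 129 hours in cholangiocarcinoma. Taking five half-lives as washout (the convention the protocol uses elsewhere, for example in exclusion criterion 18):

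- at the mean: 5 × 129 = 645 hours; 645 / 24 = about 27 days;
- at twice the mean: 5 × 258 = 1,290 hours; 1,290 / 24 = about 54 days.

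The documents do not say how long any effect on hormone levels lasts after the drug has cleared. These figures therefore do not fix the right period. They show only that a full 5-month exclusion cannot be derived from the documents.

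**The case against.** The strongest reply is that the risk is already handled. Section 6.3.2.2 tells investigators about the interaction, its lead-in says to avoid and replace, and Appendix 7 does contain non-hormonal options. An appendix is read together with the section that cites it. Section 6.3.2 also has investigators tell subjects to consult them before taking any additional medicine. This stands as a reason to call the point minor. It does not remove the point, because none of these texts changes what the UK criterion accepts.

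A second reply is that Appendix 7 defines highly effective by result. A hormonal method weakened enough to fail more often than 1% per year, or to stop inhibiting ovulation, would not meet the definition. That is right, and it is why the conclusion is that such a pair can satisfy the criterion, not that it always does. But the appendix gives the investigator no way to judge this for a woman on ivosidenib.

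Third, other protection remains: the mandatory barrier, a urine test before dosing on administration days, and the UK test at the 100-day visit. The barrier does lower the risk. The tests detect a pregnancy but do not prevent one.

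Two stronger readings are tempting, and the documents support neither. One is that women on hormonal methods are left unprotected. The protocol says only that concentrations may decrease and gives no size. The consent form is not among the documents, so what women are told cannot be seen. The other is that hormonal methods should lose credit for the whole 5 months after treatment; nothing in the documents establishes that length.

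**Conclusion.** The point holds as a minor inconsistency between a warning and an eligibility rule. As written, a combined or progestogen-only method plus a barrier can satisfy UK criterion 4 during ivosidenib treatment, even though Section 6.3.2.2 says ivosidenib may weaken it.

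Its reach is very small. It concerns UK women of childbearing potential who rely on one of those two methods. The documents do not give their number, and it may be zero: the SAP (Section 5) reports that enrollment stopped after 7 patients at all sites together, and its introduction dates the termination letter 21 August 2024. Nobody new will be screened under the criterion.

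The point may still matter for a woman already treated. If the study was stopped for reasons other than safety, which the documents do not say, Protocol Section 4.3.1 lets subjects who benefit stay on ivosidenib. The UK contraception duty also runs past the last dose.

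The conclusion rests on the wording alone. It assumes nothing about how far hormone levels fall, and it has no bearing on any endpoint, analysis set or estimate.

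**What to change.** Add to Appendix 7 and to its UK version in Appendix 13:

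> Because ivosidenib may decrease hormonal contraceptive concentrations (Section 6.3.2.2), combined and progestogen-only hormonal methods do not count as the highly effective method for criterion 4 during ivosidenib treatment and for a post-treatment period set by the clinical team from washout and induction-offset data, not exceeding the existing 5 months. Methods that still count are a non-hormonal intra-uterine device, bilateral tubal occlusion, a vasectomized partner, true abstinence and, if the clinical team confirms it, an intrauterine hormone-releasing system.

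The barrier requirement stays as it is. The clinical team has two items to settle: the length of the post-treatment period and the status of the hormone-releasing system.

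The cost is two sentences. With enrollment stopped, a letter to sites covering any woman still on ivosidenib or still in the post-treatment contraception period is enough. The downside is that a few women, possibly none, would have to change method.

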6.4. IMP Compliance

For ivosidenib, subjects will be dispensed the appropriate number of Sponsor-packaged and labeled bottles to allow for 21 ± 2 days of dosing for the first 4 cycles then for 28 ± 2 days of dosing from the Cycle 5. Alternatively, they may be dispensed appropriate bottle(s) until the next scheduled visit. The number of pill bottles dispensed and the number of tablets returned by the subject are to be counted by the Investigator or delegate and recorded. For the infusion therapies, the number of vials dispensed will be counted by the Investigator or designee and recorded in the eCRF and RTSM or an equivalent document.

Subjects will receive instructions for home administration of IMP along with a diary to record the date and time of each dose, as well as the number and strength (mg) of tablets taken.

Treatment compliance will be assessed using the drug diary and/or return of unused drug. Accountability for the IMP at the study site is the responsibility of the Investigator. The Investigator will ensure that the IMP is used only in accordance with this protocol.

Where allowed, the Investigator may choose to assign drug accountability responsibilities to a pharmacist or other appropriate individual. The Investigator or delegate will maintain accurate drug accountability records indicating the drug's delivery date to the site, inventory at the site, use by each subject, and return to Sponsor or its designee (or disposal of the drug, if approved by Sponsor). These records will adequately document that the subjects were provided the doses as specified in the protocol and should reconcile all IMP received from Sponsor.

Accountability records will include dates, quantities, batch/serial numbers, expiration dates, and subject numbers. The Sponsor or designee will review drug accountability at the site on an ongoing basis during monitoring visits. IMP must not be used for any purpose other than the present study. IMP that has been dispensed to a subject and returned unused must not be redispensed to a different subject. All unused and used IMP should be retained at the site until inventoried by the study monitor. All used, unused, or expired IMP, disposed of at the study site per the site's standard operating procedures and documented via a destruction certificate, or drug kits can be recovered from the site and, after Sponsor approval, sent to a destruction body who will destroy and provide a destruction certificate for documentation.

6.5. Discontinuation of the IMP

After the discontinuation of the IMP, the participant's treatment is left to the physician's discretion.

7. ASSESSMENT OF EFFICACY

7.1. Efficacy Measurements

Efficacy measurements performed during the study are indicated in [Table \(4.1.2\) 1](#).

Standard response criteria will be applied for disease assessments and response evaluations (RECIST v1.1 [[Table \(4.1.2\) 1](#)]). Assessments should be performed at the intervals specified in the investigation schedules and in the event of suspected disease progression.

The same method(s) of disease evaluation and the same techniques should be used throughout the study as the baseline.

7.2. Methods and Measurement Times

Response will be assessed by the Investigator or qualified designee and will be noted at each evaluation point as complete response (CR), partial response (PR), SD, progressive disease, or not evaluable (NE) ([Table \(7.2\) 1](#)).

Radiographic assessments (CT or MRI) for evaluation of disease response are to be conducted at Screening (Day -21 to Day -1), every 6 weeks (\pm 7 days) for the first 2 assessments (*i.e.*, through Week 12), and then every 8 weeks (\pm 7 days) thereafter, independent of dose delays and/or dose interruptions, and/or at any time when progression of disease is suspected. Tumor assessment frequency may be reduced to every 12 weeks 2 years after treatment initiation.

Per RECIST v1.1, response should be confirmed by repeat imaging assessment not less than 4 weeks from the date the response was first documented. The scan for confirmation of the response may be performed at the earliest 4 weeks after the first documentation of response or at the next scheduled scan (approximately 6 to 8-week interval from last scan), whichever is clinically indicated.

The Investigator should consider all lesions (target and non-target) in assessing the tumor burden at repeat imaging prior to making a decision for continuation of treatment.

Table (7.2) 1 - Imaging After First Radiological Evidence of Disease Progression

Scenario	Clinically Stable		Clinically Unstable	
	Imaging	Treatment	Imaging	Treatment
First radiological evidence of disease progression	Repeat imaging at ≥ 4 weeks to confirm disease status	May continue study treatment per Investigator discretion while waiting confirmation scan	Repeat imaging at ≥ 4 weeks to confirm disease progression per Investigator discretion only	Discontinue treatment
Repeat scan confirms disease progression	No additional imaging required	Discontinue treatment (exception upon consultation with the Sponsor)	No additional imaging required	NA
Repeat scan shows SD, PR, or CR	Continue tumor imaging assessment at scheduled intervals	Continue study treatment per Investigator discretion	Continue regularly scheduled imaging assessments	May restart study treatment if condition has improved and/or is clinically stable as per Investigator discretion

Abbreviations CR = complete response; NA = not applicable; PR = partial response; SD = stable disease.

Note: if a subject has confirmed radiological disease progression but the subject is achieving a clinically meaningful benefit, an exception to continue treatment may be considered after consultation with the Sponsor. In this case, the subject must have absence of symptoms and signs of progression of disease, absence of decline in ECOG performance status, and absence of tumor progression at critical anatomic sites. In such cases, subject should be followed for tumor assessment and safety per protocol required schedule of assessment.

7.3. Central Imaging Facility

During the Expansion phase, a central imaging facility may evaluate imaging studies and supportive clinical data in a central and independent fashion, from subjects enrolled in Safety Lead-In phase and the Expansion phase. The facility will not perform independent clinical evaluations. The central imaging facility may be chartered to establish radiographic progression and may consider selected clinical data solely to aid in the interpretation of radiographic images. A detailed site-specific Imaging Core Manual will be made available regarding scan acquisition requirements. All radiological scans acquired at all scheduled time points and any additional (unscheduled) radiological images acquired to evaluate for potential metastatic disease also may be sent to the central imaging facility. In addition, the most recent pre-treatment scans (*i.e.*, prior to screening) may also be requested, if available, from subjects in the dose escalation phase of the study. These scans will be collected and sent to a central imaging facility as detailed in the site-specific Imaging Core Manual.

The site is expected to maintain a copy of digital data for the retention period applicable to the protocol, GCP, and federal, international and/or state legal and medical requirements. The Sponsor and/or designee may retain the media until or beyond study completion.

